6.1.5. Collected data

Collected data will be recorded in the subject's e-CRF.

Physical examination data

A complete physical examination will be carried out by a physician at enrolment visit (V0), inclusion (V1) and at last visit (V2), and will be evaluated overall as "normal" or "abnormal".

Vital sign data and Electrocardiogram (ECG)

Supine blood pressure (mean of two measurements), heart rate and intra-auricular temperature will be performed at visits (V0), (V1), (V2). Blood pressure and heart rates will be recorded after at least five minutes supine.

ECG, height, weight and waist circumference will be performed only at V0.

The normal ranges used by the Biotrial are the following:

- HR : [40-100]
- ECG : PR < 220 ms, QRS < 120 ms, QTc male < 450 ms, QTc female < 470 ms

Medical histories and data

- General information (demography, eye color, hair color, corrective lenses, age of graying, age at menarche, menstruation cycle, year of the last cervical smear, pregnancies and children ages, menopause, occupation, education)
- Past and current medical and surgical history, including childhood diseases, and perinatal history (premature birth, method of delivery, breast feeding including duration, ...)
- Food consumption and nutritional intakes
- Lifestyle (smoking, alcohol, drugs habits, physical activities, travel, etc)
- Family health history
- Vaccination history (polio, hepatitis B, influenza, measles, varicella, BCG) based on the vaccination certificate
- Medication intake
- Para-medication intake (essential oils, fish oils, herbal preparation, vitamin and mineral supplementation, probiotics ...)

Standard laboratory data

Standard laboratory data from blood sample and urine test will be assessed by the investigator.

Occurrence and intensity of abnormal biology values occurring throughout the study period will be reported into the e-CRF.

Any standards laboratory parameters that the investigator judges to be clinically significant will be recorded as an adverse event. As such, clinically significant laboratory abnormalities will be followed until clinical resolution, improvement or stabilization (only relevant for standard lab repeated at V2).

7. STUDY COMPLETION AND SUBJECT REMOVAL FROM THE STUDY

7.1. Study completion

Subjects randomized to perform V2 (with biopsy or not at V1) will be considered to have completed the study after having attended visit V2.

Subjects randomized to only perform V1 will be considered to have completed the study after having attended visit V1.

7.2. Criteria for withdrawal from the study and replacement policy

If one or more of the following occurs, the subject will be discontinued from study:

- At any time, if the subject decides to withdraw his/her consent
- At any time, if the subject develops a non-inclusion criterion (e.g. development of an acute disease between V0 and V2) for example:
 - Clinically significant pulmonary, cardiovascular, hepatic or renal functional abnormality, as determined by physical examination or laboratory tests
 - Intra-auricular temperature $\geq 38.4^{\circ}\text{C}$ between V0 and V2.
 - Pregnant woman: in case of pregnant woman, the data from the collected sample won't be use in the final statistical analysis.
- At any time, if the subject develops an AE or an SAE (see section 11)
- At any time, for safety reasons at the investigator's discretion.

If a subject is withdrawn from the study (i.e for subjects performing V2: ceases participation in the study prior to completion of the V2 assessments planned in the protocol), the primary reason should be recorded in the end of study form in the Case Report Form (CRF).

The investigator will provide or arrange for appropriate follow-up (if required) for subjects withdrawing from the study. If the subject has withdrawn due to an AE or SAE the Investigator should follow the procedures documented in Section 11.

In the event of a premature withdrawal, the subject will be replaced by a subject of the same gender and age decade.

If blood, urinary or ECG assessments lead to exclude the subject from the study after V0, he/she will be compensated for his participating in the first visit.

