9.3. Phenotypic assessment of the donors (baseline)

12mL of blood sample will be collected at inclusion visit (V1) and analyzed at local center for the assessment of the phenotypic of the donors to have a baseline for each donor:

Serology

4mL will be collected for serology assessments will include: Influenza.

Immunology assessments

8mL will be collected for immunology assessments that will include serum immunoglobulins (IgM, IgG, IgA, IgE).

Any laboratory parameters that the investigator judges to be clinically significant will be recorded as an adverse event. As such, clinically significant laboratory abnormalities will be followed until clinical resolution, improvement or stabilization (only relevant for standard lab repeated at V2).

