11. SECURITY AND SAFETY EVALUATION

11.1. Definitions

Adverse Events (AE)

Any untoward medical occurrence in a clinical research subject and which does not necessarily have a causal relationship with this research.

Adverse Reaction (AR)

Any untoward medical occurrence in a clinical research subject and which has a causal relationship with this research.

Serious Adverse Event (SAE)

A serious adverse event is any untoward medical occurrence that:

- Results in death,
- Is life threatening (subject at risk of death at the time of the event),
- Requires inpatient hospitalization or prolongation of existing hospitalization,
- Results in persistence or significant disability/incapacity, or
- Is a congenital anomaly/birth defect
- Medical and scientific judgment should be exercised in deciding whether expedited reporting is appropriate in other situations, such as important medical events that may not be immediately life-threatening or result in death or hospitalisation but may jeopardise the subject or may require intervention to prevent one of the other outcomes listed in the definition above. These should also usually be considered serious (ICH E2A).

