11.2. Expected Adverse events

The only unwanted effects expected during the participation of the subjects are:

- Those related to the blood collection (discomfort at puncture site, transient hematoma, more rarely faintness or syncope)
- Those related to the skin biopsy (Allergic reaction due to the local anesthesia, local infection, bleeding, scar risk, vagal faintness)
- Those related to the nasal swab (low bleeding, irritation)

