11.3. Reporting of the Adverse Events

Any Adverse events occurring during the study will be reported in the CRF appropriate sections. For each adverse event, relevant information should be reported in the CRF including the nature, the timing of event occurrence and resolution, the severity, the outcome, the relationship to the research, the measures taken for the subject.

The severity of the event will be evaluated by the following scale:

- Mild: does not interfere with the usual subject activities
- Moderate: partially prevents the subject to perform his/her usual activities
- Severe: prevents totally the subject to perform his/her usual activities

The investigator should follow each adverse event until the event has resolved to baseline grade or better, the event is assessed as stable by the investigator, the subject is lost to follow up, or the subject withdraws consent. Every effort should be made to follow all serious adverse events considered to be related to study drug or trial-related procedures until a final outcome can be reported.

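### Section 7.2 makes any adverse event, however mild, expected or unrelated, a mandatory reason for discontinuation (minor)

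*Protocol*

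**What the plan says.** Protocol section 7.2 opens its list of withdrawal criteria with "If one or more of the following occurs, the subject will be discontinued from study". The list is mandatory and any single item is enough. The third item reads "At any time, if the subject develops an AE or an SAE (see section 11"). Withdrawal for safety at the investigator's discretion is a separate item and does not qualify this one. Developing a non-inclusion criterion is also a separate item.

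Section 11, to which the item points, gives these definitions:

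- Section 11.1 defines an adverse event as "Any untoward medical occurrence in a clinical research subject and which does not necessarily have a causal relationship with this research".
- Section 11.2 names, among the expected events, "Those related to the blood collection (discomfort at puncture site, transient hematoma, more rarely faintness or syncope").
- Section 11.3 grades events from the lowest level up: "Mild: does not interfere with the usual subject activities".

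Laboratory findings can also become adverse events. Section 9.3, which covers the V1 baseline sample, says "Any laboratory parameters that the investigator judges to be clinically significant will be recorded as an adverse event", and that sample includes serum immunoglobulins.

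Section 7.2 also has each prematurely withdrawn subject replaced by one of the same gender and age decade. The synopsis (item 13) gives the purpose: 500 complete V2 observations.

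**The concern.** A mandatory withdrawal rule needs a threshold, and this one has none. Every V2 donor has blood drawn at V1, and many may have a skin biopsy. The protocol itself expects puncture-site discomfort, bruising and minor bleeding from these procedures. Read literally, each such event ends participation.

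Two things are at stake. First, donors would be withdrawn without medical or scientific need. Each replacement means another person going through the V1 procedures: 12 mL + 75 mL = 87 mL of blood (section 6.1.3) and possibly a biopsy. Second, section 1.3 describes the repeat collection at V2 as a validation sample. If donors with any event are removed, that sample leans towards donors who had none. Replacement within gender and decade restores the number but not the mix.

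If the site does not follow the rule literally, the criterion actually used for each discontinuation is not written down, and keeping a donor with a bruise departs from the protocol.

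**Working it through.** **Step 1: does any text supply a threshold?**

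| Possible limit | Where it would be | What is there |
|---|---|---|
| Severity | 11.3 | Three grades; none tied to withdrawal |
| Causality | 11.1 | Unrelated events are included |
| Expectedness | 11.2 | Expected events are listed, not exempted |
| Investigator judgment | 7.2 | A separate item |

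No limit is found. A transient hematoma is an expected event (11.2), can be mild (11.3), and so triggers the item in 7.2. The same list sets specific limits elsewhere: an intra-auricular temperature of at least 38.4°C, and organ abnormalities that are clinically significant. Those limits do little work if any lesser event already ends participation.

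**Step 2: the protocol's own figures.**

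- V2 target (section 4.1): 5 decades × 2 genders × 50 = 500. This agrees.
- Precision for a mean (section 12.2), as 1.96/√n in SD units: n = 1000 gives 0.062; n = 100 gives 0.196, stated as 0.20. Both agree. These refer to the V1 sample.

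**Step 3: size per unit of event rate.** The protocol gives no adverse event rate.

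- Each 1% of V2 donors with an event: 0.01 × 500 = 5 donors.
- One event in a gender-by-decade V2 cell: 1/50 = 2% of that cell.

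**Step 4: illustration with assumed rates.** The rates q below are assumptions, taken wide because the definition has no severity floor. Withdrawn from the first 500 = 500q. Replacements needed = 500/(1 − q), rounded up, minus 500, if replacements have the same rate.

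| Assumed q | Withdrawn | Replacements | V2 half-width with replacement | Without replacement |
|---|---|---|---|---|
| 2% | 10 | 11 | 1.96/√500 = 0.088 SD | 1.96/√490 = 0.089 SD |
| 10% | 50 | 56 | 0.088 SD | 1.96/√450 = 0.092 SD |
| 30% | 150 | 215 | 0.088 SD | 1.96/√350 = 0.105 SD |

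The last column is a bound only, because the protocol plans replacement. The cost therefore lies in the second and third columns and in who remains in the V2 sample, not in precision.

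**The case against.** The strongest reply is that this is a drafting slip that no site would apply literally. Section 7.2 says what to do if a subject has withdrawn because of an adverse event, which sounds conditional. Section 11.3 has each event followed to resolution or stability. Section 6.1.4 schedules an adverse event evaluation and a biopsy-site check at V2. A slip is plausible, but none of these texts says that a donor with an event continues. The conditional sentence fits mandatory withdrawal, follow-up can go on after withdrawal, and an evaluation at V2 can simply find new events. The rule stands as written.

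Other parts of the reply do hold, and they rule out stronger readings that a reader might infer:

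- **That the protocol contradicts itself.** Section 8 allows treatment of a concomitant health problem, section 8.2 concerns exclusion from analysis, and section 6.1.5 says "clinically significant laboratory abnormalities will be followed until clinical resolution, improvement or stabilization (only relevant for standard lab repeated at V2"). All three are compatible with discontinuing the donor.
- **That every V1 immunoglobulin value judged clinically significant would be lost only because of this item.** A confirmed or suspected immunodeficient condition is non-inclusion criterion 11.3, and developing one triggers the separate second item of 7.2. Some of these donors would leave after any rewording, and keeping the cohort healthy is intended.
- **That all losses fall before V2.** Sections 6.1.3 and 6.1.4 schedule no adverse event contact between V1 and V2. Donors are only told to phone about biopsy healing. Many mild events would come to light at V2, where the rule could still stop the visit.
- **That the study loses precision.** Replacement keeps V2 at 500, and section 12.2 states no precision for V2.

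**Conclusion.** The point holds as a minor one. Section 7.2 states a mandatory rule without a threshold. Followed as written, it withdraws V2-assigned donors, before or at V2, for trivial events that meet no non-inclusion criterion. The consequences are avoidable withdrawal, extra donors exposed to study procedures, and some selection of the V2 validation sample towards donors without adverse events.

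The size is unknown: 5 of 500 for each 1% of V2 donors with an event, and the counts at 2% to 30% rest on assumed rates. The V2 count, the V1 sample of 1000 and the precision in section 12.2 are unchanged with the planned replacement. Adverse event withdrawal does not by itself remove V1 data either: among the withdrawal reasons in 7.2, only pregnancy is said to take collected data out of the analysis. Donors assigned to V1 only complete the study at V1 (section 7.1), so the V2 consequence concerns only the 500 assigned to V2.

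**What to change.** Reword the item in section 7.2 to: *an SAE, or an AE that in the investigator's judgment makes continuation unsafe or that meets a non-inclusion criterion*. Add: *Other AEs, including mild expected procedure-related AEs (11.2), are recorded and followed under 11.3 and the subject continues.*

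An expected event that does meet a non-inclusion criterion, such as a local infection at the biopsy site that counts as a current acute infection (criterion 11.8), still leads to withdrawal under the first sentence. The new text partly overlaps with the non-inclusion and safety items already in 7.2; its substance is the limit on the adverse event item.

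The cost is one reworded item and one added sentence. The downside is reliance on the investigator's judgment, which 7.2 already uses in its safety item.

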8. CONCOMITANT MEDICATIONS

It is recommended that the subject does not modify his/her treatment during the study. Nevertheless he may receive any treatment required in case of a concomitant health problem.

For all concomitant treatments taken during the study, the following information must be collected in the relevant section of the e-CRF:

- The name of the treatment and its form,
- The reason for prescription,
- The route of administration,

-
- The daily dose,
 - The duration.

8.1. Authorized treatment

Hormonal contraception and HRT for menopause are authorized during the study, provided these treatments were started at least 3 months prior to inclusion (V1) and are kept stable until the end of the study.

Inhaled and topical steroids are allowed with the exception of medium or high dose inhaled glucocorticosteroids for asthma (see non-inclusion criteria).

Treatment with low dose of aspirin (maximum 250 mg/daily) is allowed but should be kept stable until end of study.

Long term prophylactic tamoxifen (or related molecules) for breast cancer in women who are disease free 3 years or more after the breast cancer treatment is allowed and should be kept stable until end of study.

8.2. Prohibited treatments

The following therapies are not allowed during the study:

- Anti-depressant
- Immunosuppressant or other immune-modifying drugs
- Chemotherapies and treatments against cancer except long term prophylactic tamoxifen (or related molecule) for women who are disease free 3 years or more after the treatment for breast cancer
- Anticoagulants (e.g. warfarin derivatives or heparin or antiplatelet medications with the exception of low dose of aspirin)
- NSAIDs including aspirin [exception for low dose aspirin, see 8.1]
- Any anti-diabetic treatment
- Oral corticosteroids at a dose equivalent to 20 mg/day of prednisone or equivalent for persons for > 2 weeks
- Antibiotics
- Antiseptics (intestinal, nasal or respiratory)
- Vaccination
- Blood products or immunoglobulins
- Investigational product
- Bisphosphatate

Any subject taking one of these prohibited treatments will be excluded from the study analysis.

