6.1.1. Eligibility

The eligibility of the subjects will be determined in accordance with the sites procedures and the following criteria will be checked by phone:

- 1/ Healthy male or female aged between 20 and 69 years (≥ 20 and ≤ 69 years)
- 2/ Metropolitan French origin for 3 generations
- 3/ Covered by a social security regimen or beneficiary of a social security regimen
- 4/ For women, not pregnant or breastfeeding
- 5/ BMI ≥ 18.5 and ≤ 32 kg/m² (Appendix 18.6)
- 6/ Access to a consistent means of telephone contact, which may be either in the home or at the workplace, land line or mobile
- 7/ Must understand spoken and written French

The site will use their subjects' registries in order to identify those subjects who meet the main eligibility criteria. The subjects' eligibility will be assessed and confirmed through a telephone interview.

In addition, the subjects could be recruited by means of an advertising campaign.

Subjects will be stratified according to age and gender in a 1:1 ratio. The stratification will be performed through a centralized stratification system. The stratification per group should be stopped once 100 subjects per strata were included. In addition, a randomization will be done at V1 to select 500 subjects who will complete the V2 (100 in each decade with 50% male and 50% female) and up to 500 subjects from these V2 subjects to perform a biopsy at V1.

A preliminary information meeting will take place upstream to the visit V0. At this visit the research will be explained by the investigator.

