6.1.3. Inclusion visit (V1)

The inclusion visit (V1) will take place 4 to 14 days after (V0). The subject will have to be on an empty stomach for at least 6 hours. In addition the subject must not have made any physical exercise within 8 hours before the visit V1.

A unique inclusion number (randomization number) will be attributed to every included subject and the volunteer will be informed of the randomization outcome (i) to perform V2 with or without biopsy at V1 (ii) to perform only V1 without biopsy

After the subject has been included, the following procedures will be performed:

- Clinical assessments
 - Physical examination ;
 - Vital signs measurements ;
 - Blood pressure (2 supine measurements);
 - Heart rate;
 - Body temperature;
- Other assessments;
 - Lifestyle questionnaire including exercise habits ;
 - Concomitant treatments;
 - AE/SAE evaluation;
- Blood sample collection for (see appendix 18.5):
 - phenotypic assessment (baseline): 12mL
 - trial objectives: 75 mL
 - Genetic analysis (25mL);
 - TruCulture® - immune assays (50mL);
- Stools sample (collected at home within 24h before V1);
- Nasal swab;
- Skin punch biopsy (Appendix 18.2) for up to 500 subjects: for some subjects, the pose of strip or stitch will be made if clinically required. In case of stitches, they will be removed between 7 to 14 days after the biopsy and before V2.

Appropriate material and procedure for stool sampling will be given to the donor who will perform V2. Stool collection will be performed at home before or after returning at V1 (within 24hours before the visit and up to 2 days after).

The subject will be asked if he/she has joined the study Nutrinet - Santé.

The subject will be instructed to phone the center in case of any issue in biopsy site healing.

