6.1.4. End of study visit (V2)

This visit will only occur for the subjects who will have been biopsied at V1. The visit (V2) will take place 28 days after (V1). A time windows of +/- 14 days is allowed then visit (V2) can take place maximum 42 days after (V1) and minimum 14 days after (V1).

The subject will have to be on an empty stomach for at least 6 hours. In addition the subject must not have made any physical exercise within 8 hours before the visit V1.

The following investigations will be conducted at the end of study visit:

- Clinical assessments;
 - Physical examination ;
 - Vital signs measurements;
 - Blood pressure (2 measurements);
 - Heart rate;
 - Body temperature;
- Other assessments;
 - Concomitant treatments ;
 - AE/SAE evaluation;
- Skin biopsy site examination, if applicable;
- Urine pregnancy test for women of childbearing potential;
- Blood sample collection for (see Appendix 17.5):
 - standard analysis (8mL) (see Appendix 17.5):
 - Haematology and CRP;
 - trial objectives:75mL (see appendix 18.5)
 - Genetic analysis (25mL);
 - TruCulture® - immune assays (50mL);
- Stools sample (collected at home within 24 h before (V2));
- Nasal swab;
- End of study assessment.

The urine pregnancy test will be the first to be performed. In case of positive test, the subject is withdrawn from the study and no other tests will be performed.

The subject will be asked if he/she has completed the study Nutrinet.

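### Section 8.2 excludes the whole donor for a prohibited treatment, so an intake after V1 deletes V1 data already collected, and only in the half randomised to V2

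*Protocol*

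**What the plan says.** Section 8.2 opens its list with "The following therapies are not allowed during the study" and closes it with "Any subject taking one of these prohibited treatments will be excluded from the study analysis". The list includes NSAIDs (low-dose aspirin excepted), antibiotics, antiseptics and vaccination. Nothing limits the exclusion to samples taken after the treatment, and no other section keeps the earlier ones.

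How long a donor is in the study depends on the draw. Section 6.1.1: "a randomization will be done at V1 to select 500 subjects who will complete the V2". Section 7.1 then gives two end points: "Subjects randomized to perform V2 (with biopsy or not at V1) will be considered to have completed the study after having attended visit V2" and "Subjects randomized to only perform V1 will be considered to have completed the study after having attended visit V1". Section 6.1.4 places V2 at 28 days after V1, give or take 14.

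Section 7.2 discontinues donors who develop a non-inclusion criterion and replaces those withdrawn with a donor of the same sex and decade. Section 8 allows needed care: "Nevertheless he may receive any treatment required in case of a concomitant health problem".

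**The concern.** A V1 blood sample or nasal swab cannot be changed by a drug taken three weeks later. Under 8.2 that drug still removes the sample from the analysis if the donor was drawn for V2, and does nothing if the donor was not. Two donors with the same V1 data and the same later intake are treated differently because of a lottery that has nothing to do with data quality.

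The primary objective concerns the determinants of immune variance in healthy people. Donors who need anti-infective or anti-inflammatory drugs soon after V1 plausibly differ in immune phenotype at V1. Dropping them afterwards selects on something related to the outcome. Because this happens in one half only, the pooled V1 set represents neither all eligible donors nor donors who stayed untreated in the following weeks.

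**Working it through.** **Inputs from the protocol.** 1000 donors at V1, 100 per sex-by-decade cell; 500 drawn for V2, 50 per cell (4.1, 6.1.1). Further time under the rule after V1: 14-42 days for the V2 half, none for the V1-only half (6.1.4, 7.1).

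**Inputs assumed.** p, the share of the V2 half taking a listed product between V1 and V2: 10-30%. d, the V1 difference between later users and non-users: 0.2-0.5 SD. Neither is in the documents. As a plausibility check on p, a constant rate of r episodes per person-year gives 1 - exp(-r × days/365). With r = 1 to 2 (assumed) this is 7-14% over 28 days and 11-21% over 42 days.

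**Step 1: reproduce the stated precision (12.2).** Half-width for a mean = 1.96/√n SD.
- n = 1000: 0.062 SD (stated 0.062).
- n = 100: 0.196 SD (stated 0.20).

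**Step 2: precision under 8.2 without replacement.** V1 data sets lost = 500p. Total = 500 + 500(1 - p). Cell = 50 + 50(1 - p).

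| p | V1 data sets lost | Total | Half-width, total (SD) | Cell | Half-width, cell (SD) |
|---|---|---|---|---|---|
| 10% | 50 | 950 | 0.064 | 95 | 0.201 |
| 20% | 100 | 900 | 0.065 | 90 | 0.207 |
| 30% | 150 | 850 | 0.067 | 85 | 0.213 |

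**Step 3: selection.** If non-users have V1 mean m, the whole V2 half has mean m + p·d. Keeping non-users only moves it by p·d:
- p = 10%: 0.02 to 0.05 SD.
- p = 30%: 0.06 to 0.15 SD.

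The V1-only half does not move. With full replacement the halves are of equal size and the pooled shift is p·d/2: 0.01 to 0.025 SD at 10%, and 0.03 to 0.075 SD at 30%. Without replacement the weight is 500(1 - p)/total, giving 0.010 to 0.024 SD at 10% and 0.025 to 0.062 SD at 30%. Replacement therefore does not reduce the shift, since replacements who are drawn for V2 are filtered in the same way.

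**Step 4: who is replaced.** Several listed products, or the conditions they treat, are also non-inclusion criteria in 4.3 (antibiotics and antiseptics, vaccination, blood products, anticoagulants, treated depression). These donors would be discontinued and replaced under 7.2. Brief NSAID use differs. Criterion 13 concerns intake beyond two weeks, or any intake in the week before a biopsy, whereas 8.2 names NSAIDs with no minimum duration. A donor with a short intake after V1 may complete V2 and then be dropped without a replacement.

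**The case against.** The best case for the plan has four parts.

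- **Replacement.** For most listed products 7.2 brings in another donor, and the synopsis aims at 500 complete V2 observations. This stands for the counts: with full replacement the cell sizes in step 2 do not arise. It does not stand for the discarded V1 data or for the selection.
- **Small effect on assumed rates.** This stands. The precision loss is slight, and the pooled shift with replacement exceeds the 0.062 SD half-width only near the top of both assumed ranges (0.075 SD at 30% and 0.5 SD).
- **Healthy donors are the target.** Someone treated for infection days after V1 may have been incubating it at V1, and Appendix 18.1 already excludes donors with raised activation markers. This is a fair reason to examine such donors. It does not justify the rule as written, which leaves equivalent V1-only donors in.
- **An analysis plan, not shown here, could narrow the rule.** It could, but it would then contradict an explicit protocol sentence.

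Some stronger readings do not hold. A reader might infer that 8.2 touches only the V2 half; intake between V0 and V1 can exclude anyone, and only the loss of V1 data through a later event is confined to that half. A reader might infer that section 8 contradicts 8.2; it permits care, while 8.2 states the consequence for analysis, and the two are compatible. A reader might take all V1 samples to be beyond the reach of a later drug; V1 stool may be collected up to two days after the visit (9.4.2), so an intake in those days can affect it.

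**Conclusion.** The point holds. Followed as written, 8.2 discards V1 data because of an event after sampling that is observed in one randomised half only, and nothing in the protocol keeps those data.

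The main harm is selection, not lost precision. At an assumed 10-30% use without replacement, 50-150 V1 data sets go and the V1 cell half-width rises from 0.196 to 0.201-0.213 SD. With full replacement the counts recover and only the selection remains. The size of the selection rests on assumed p and d throughout.

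A reader might add the shrinking of the V2 cells to the bill. It does not belong there: V2 samples taken after an intake would also leave the primary V2 analysis under a sample-level rule.

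**What to change.** Replace the closing sentence of 8.2 with a sample-level rule, for example: *A sample collected after an intake of a prohibited treatment during the study is excluded from the primary analysis of that visit. Samples collected before the intake are kept, each judged by its own collection date, including stool. Germline genotype data are kept in all cases.*

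Add start and stop dates to the concomitant-treatment fields in section 8, which currently ask for duration but not dates. Without dates the rule cannot be applied.

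Add a sensitivity analysis of the V1 results with and without donors who took a prohibited treatment after V1. This also addresses infection that may have been incubating at V1.

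Cost: two extra e-CRF fields if dates are not already captured, and one additional analysis. No extra subjects or samples are needed. The list of prohibited treatments is not questioned.
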